The power analysis for the primary hypothesis was conducted following the recommendations of Diggle et al. for mixed effects models. Using a two-sided alpha of .05, an estimated intraclass correlation of .7 between the repeated measurements, and a 15% attrition rate by month 6, we will have 85% power to detect a moderate effect of the intervention ($d = .4$) with a sample size of 111 patients in each group.

6. Explain procedures that will involve the subject

As part of their treatment experience, all patients who provide informed consent will continue to receive all other standard TUH medical treatment. Enrolled participants will be **randomly assigned** to either Treatment as Usual (TAU) via Temple's standard Advantage program or to Specialized Community Disease Management (SCDM). Random assignment will be stratified by 1) severity of DSM-V SUD (Low or High) as measured by the Mini-International Neuropsychiatric Interview Plus 5.0 (MINI, Sheehan et al., 1998), 2) index medical condition (CHF or Other), and 3) frequency of previous hospital utilization (high utilizer vs. non-frequent utilizer). Hospital utilization will be considered frequent if the patient has had 5 or more hospitalizations in the past year, or 2 or more hospitalizations in the past 6 months for patients with CHF. Randomized participants will receive brief intervention and referral to SUD treatment as part of their discharge planning.

Intervention Procedures

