For the 1-month interviews, we will ask the first 3 TAU participants and first 3 SCDM participants who enroll in the study to participate in this interview. Should any participant decline, we will ask the next participant from that condition who enrolls in the study. For the 3-month interviews, we will ask the first 3 TAU participants and first 3 SCDM who complete the 3-month assessment but did not complete a 1-month interview to participate. As with the 1-month interviews, should any participant decline, we will ask the next participant from that condition who completes the 3-month assessment. Participants who agree to be interviewed will complete a separate informed consent for this portion of the study, as outlined in Item 9 below. Participants will be paid \$50 for their time and travel to the interviews.

7. Identify the sources of research material obtained from individually identifiable living human subjects in the form of specimens, records, or data.

Variable	Purpose	Instrument	Time Points			Completed by:			
			S	B	3	6	Patient	BHC	RA
Drug and Alcohol Problems	Screen/Urn Randomize	AUDIT, DAST-10, MINI	X					X	X
Substance Use	Primary Hypothesis	Timeline Followback, Uritox Quick Test, Medical Records		X	X	X	X		X
Intervention & Treatment Engagement	Secondary Hypothesis A	NSMOS		X	X	X	X		X
HIV Risk Reduction	Secondary Hypothesis B	HIV-RA		X	X	X	X		X
Rehospitalization	Exploratory Hypothesis	Temple Hospital Utilization Review				X			X

Patient Demographics and Medical Functioning	Covariates	ASI, Healthy Days	X	X	X	X		X
Patient Mental Health Functioning	Covariates	PHQ-9, ACES (Baseline only)	X	X	X	X		X
Satisfaction	Covariate	Client Satisfaction			X	X		X
Social Support	Covariate	MOS-SSS-6	X	X	X	X		X
Quality of Life	Covariate	Q-LES-Q-SF	X	X	X	X		X
Distress Tolerance	Covariate	DTS	X			X		X
Sensation Seeking	Covariate	BSSS	X			X		X

Screening Instruments

Alcohol Use Disorders Identification Test (AUDIT). The AUDIT (Babor et al., 2007) was developed by the World Health Organization to serve as a brief screening instrument and includes questions on frequency and alcohol problems and dependence (Allen et al., 1997, Reinert & Allen, 2002, Saunders et al., 1993).

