Drug Abuse Screening Test (DAST-10). The DAST-10 (Skinner, 1982) is a 10-item face valid self-report measure of problematic substance use that is utilized for clinical screening and treatment/evaluation research and which surveys potential involvement with drugs during the past 12 months (Allen et al., 1997; Maisto et al., 2000; Saunders et al., 1993; Yudko, Lozhkina & Fouts, 2007).

DSM-V SUD Diagnosis: MINI Plus 5.0. The MINI is a short structured diagnostic interview developed in the United States and Europe for DSM-IV and ICD-10 psychiatric disorders (Sheehan et al., 1998). The MINI has become the structured psychiatric interview of choice for psychiatric evaluation and outcome tracking in clinical psychopharmacology trials and epidemiological studies. We will modify the MINI to meet DSM-V criteria for SUD. In DSM-V, the 7 DSM-IV items for dependence and 4 items for abuse have been merged into a single entity of 11 items called a “Substance Use Disorder” but with the following two changes - the abuse item of recurrent legal problems will be removed and an item for craving or strong desire to use will be added (American Psychiatric Association, 2013). A diagnosis of SUD requires 2 or more of the 11 items, and SUDs have three levels of severity: 2-3 items = mild, 4-5 = moderate, and 6+ = severe; any diagnosis of SUD results in study eligibility.

Patient Outcomes

90-Day Timeline Followback (TLFB): The TLFB (Sobell & Sobell, 1992) is a structured interview which helps patients recall their substance use to reflect a 90-day period. Patients are presented with a calendar representing the past 90 days, and the interviewer helps the patient anchor the calendar with memorable events to reconstruct their use (dates, amounts) over the designated period. *Administered at 0,3,6 months.*

Urine Toxicology Results: We will record the results of participants’ urine toxicology screens from medical charts. We will record results for the following illicit substances: cocaine, opiates, amphetamines, methamphetamines, benzodiazepines, cannabis, barbiturates, PCP, and Blood Alcohol Content (BAC). *Administered at Baseline only.*

Urine testing: Urine drug testing will be done using kits that test for cocaine, opiates, amphetamines, methamphetamines, benzodiazepines, cannabis, barbiturates, and PCP. These will be purchased from ACON International. These kits provide a rapid (5-minute) on-site urine test. *Administered at 0,3,6 months.*

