Study Title: Specialized Community Disease Management to Reduce Substance Use and Hospital Readmissions

NCT Number: NCT02059005

Document Date: June 30, 2017

Data Analysis Plan

Analyses will compare outcomes for the TAU and SCDM groups. We will employ remedial measures such as power transformations when necessary. We will confirm that the groups do not differ at baseline on relevant background variables using t-tests for continuous variables and chi-square tests for discrete or ordinal responses. The randomization process should minimize the need for the inclusion of covariates to reduce bias in the treatment comparisons ¹. However, relevant covariates will be considered for inclusion in the analyses to improve the precision of estimation of the effects ².

Power Analysis. The power analysis for the primary hypothesis was conducted following the recommendations of Diggle et al. ³ for mixed effects models. Using a two-sided alpha of .05, an estimated intraclass correlation of .7 between the repeated measurements, and a 15% attrition rate by month 6, we will have 85% power to detect a moderate effect of the intervention ($d = .4$) with a sample size of 111 patients in each group (222 altogether).

Primary hypothesis: Patients assigned to the SCDM condition will report significantly fewer days of substance use than patients assigned to TAU. Using TLFB data, we will create a variable for days of any substance use by combining all drug types and alcohol. Urine samples collected at months 3 and 6 will be used to confirm reports of drug use. Provided that the rate of disagreement between urine results and self-report is acceptable (below 15%), we will analyze days of substance use as a unitary variable. A linear mixed effects model ² will be used to examine days of self-reported drug use in the past 30 days at each follow-up assessment. Mixed effects models have advantages over conventional repeated measures methods in that they allow for missing observations, accommodate measurements made at different time points, provide greater flexibility in modeling the variance-covariance matrix, and permit the estimation of group and random subject-specific effects. The model will include terms for condition, assessment point, and their interaction along with any necessary covariates including the number of days of use reported at the baseline. The analysis will be conducted using

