SAS's PROC MIXED. Should the rate of disagreement between urine and self-report exceed acceptable standards; we will analyze the urine results as the primary outcome. However, the literature indicates that self-report of substance use is generally quite accurate ^{4,5}.

Secondary hypothesis (a): Patients assigned to the SCDM condition will exhibit greater reductions in days of hospitalization and acute emergency care over the six-month period than patients assigned to TAU. A linear mixed effects model ² will be used to compare participants in the two groups on the days of inpatient and ED utilization in the past 90 days at the 3 and 6-month follow-up assessments. The model will be similar to that outlined for the primary hypothesis.

Secondary hypothesis (b): Patients assigned to the SCDM condition will demonstrate higher rates of engagement in substance abuse treatment than patients assigned to TAU. A linear mixed effects model ² will be used to compare patients in the two groups on the number of treatment sessions attended in the past 90 days at the 3 and 6-month assessments, similar to that outlined for the primary hypothesis.

Exploratory hypothesis: Patients randomized to SCDM will demonstrate a) reduced HIV transmission risk behaviors, and b) greater incidence of HIV testing over the 6 month follow-up than patients randomized to TAU. Secondary efficacy analyses will be conducted to examine the effects of the intervention on HIV related behaviors. A linear mixed effects model ² will be used to compare the two groups' RAB scores (i.e., total, sex, drug) at months 3 and 6. The baseline response will be included as a covariate. A logistic regression model will be employed to test differences in incidences of testing.

References:

1. Tabachnik B, & Fidell, L.S. *Using multivariate statistics*. Boston, Massachusetts: Allyn and Bacon; 1994.

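### No SAP model names the three factors used to stratify allocation: this causes no bias and no power shortfall, but it forgoes some precision and leaves the model not fully prespecified

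*SAP*

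**What the plan says.** **Allocation.** Protocol item 6 reads "Random assignment will be stratified by 1) severity of DSM-V SUD (Low or High"), and adds index medical condition (CHF or other) and prior hospital utilization (high or non-frequent). The measures table in item 7 labels the screening instruments "Screen/Urn Randomize", which points to urn allocation.

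**Coding of the strata.** Item 6 uses two severity levels. The MINI description in item 7 has three ("2-3 items = mild, 4-5 = moderate, and 6+ = severe"), and no Low/High cut is given. For utilization, item 6 says "Hospital utilization will be considered frequent if the patient has had 5 or more hospitalizations in the past year" and adds a separate rule for CHF patients, so this factor depends in part on index condition.

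**Analysis.** The SAP's opening paragraph says "The randomization process should minimize the need for the inclusion of covariates to reduce bias in the treatment comparisons". It then adds, as a contrast, that "relevant covariates will be considered for inclusion in the analyses to improve the precision of estimation of the effects". For the primary hypothesis it says "The model will include terms for condition, assessment point, and their interaction along with any necessary covariates including the number of days of use" at baseline; baseline days of use is the only covariate named there. The hospital and emergency-care model is described only by "The model will be similar to that outlined for the primary hypothesis", and the treatment-session model likewise refers back to the primary one. The HIV-risk model names its own baseline score. The HIV-testing logistic model names no covariate.

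**The concern.** Analysing a trial by the factors it was randomized on is the usual default. Stratified allocation makes the arms more alike on those factors than chance would. A model that ignores them leaves their variation in the residual, so it reports a standard error larger than the true sampling variability of the estimate. The benefit of stratifying is then partly lost.

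The second issue is prespecification. The SAP gives no covariate list, no selection rule and no definition of a necessary covariate. Two analysts could both follow it exactly, one including all three factors and the other none, and report different standard errors and p-values for the primary outcome.

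**Working it through.** **Inputs from the SAP power paragraph:** two-sided alpha .05, intraclass correlation .7, 15% attrition, d = .4, 111 per arm, stated power 85%. Two follow-up measures (months 3 and 6) are inferred from the assessment schedule in Protocol item 6; the power paragraph does not give the number.

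**Step 1. Reproduce the plan's figure.** With SD = 1, the mean of two follow-ups correlated .7 has variance (1 + .7)/2 = .85.
- Patients per arm for 85% power: 2 × (1.960 + 1.036)² × .85 / .4² = 95.4, or 95.4/.85 = 112.2 after attrition, against 111 stated.
- With 111 × .85 = 94.35 per arm, SE = √(2 × .85/94.35) = .1342 and power = Φ(.4/.1342 − 1.960) = 84.6%, against 85% stated.
- One measure would need 133 per arm and three would need 106; neither fits.

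The plan's figure therefore comes from a formula with no strata and no baseline term.

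**Step 2. Effect of omitting the strata.** Let R² be the share of the variance left after baseline that the strata explain. The documents do not give it, so .05, .10 and .20 are assumed. Let r be the correlation of baseline with each follow-up, so the residual variance of the follow-up mean is V = .85 − r². This is .85 at r = 0, .60 at r = .5 and .36 at r = .7. V = .85 also covers the case where d = .4 is already baseline-adjusted. Under exact balance:
- reported SE without strata: s = √(2V/94.35)
- true SD of the estimate: s√(1 − R²)
- power without strata: Φ[(.4 − 1.960s)/(s√(1 − R²))]
- power with strata: Φ[.4/(s√(1 − R²)) − 1.960]
- SE ratio: 1/√(1 − R²) = 1.026, 1.054, 1.118

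Example, V = .85 and R² = .10: s = .1342 and true SD = .1273. Power is Φ[(.4 − .2631)/.1273] = .859 without strata and Φ[.4/.1273 − 1.960] = .881 with them.

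| Case | R² | Power without | Power with | Points forgone, exact balance | Points forgone, simulated urn |
|---|---|---|---|---|---|
| V = .85 | .05 | .852 | .864 | 1.1 | 1.0–1.1 |
| | .10 | .859 | .881 | 2.2 | 2.5–2.8 |
| | .20 | .873 | .915 | 4.2 | 5.7 |
| r = .5 | .05 | .948 | .953 | 0.5 | 0.6–0.7 |
| | .10 | .953 | .962 | 1.0 | 1.3–1.4 |
| | .20 | .962 | .977 | 1.6 | 2.4–2.6 |
| r = .7 | all three | above .99 | above .99 | 0.1 or less | 0.2 or less |

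The power columns are the closed form. The urn column is from 20,000 simulated trials per setting, with assumed urn rules and assumed stratum prevalences of 50%, 30% and 40%. In those simulations the SE ratio was 1.02, 1.05 and 1.11. The mean estimate was .40 with or without strata. Power without strata was .84–.85 at V = .85, .94–.95 at r = .5 and above .99 at r = .7.

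**Step 3. False-positive rate with strata omitted.** Under exact balance it is 2[1 − Φ(1.960/√(1 − R²))] = .044, .039 and .028. Under the simulated urn, which balances only approximately, it is .045–.050, .043–.046 and .037–.042. Neither exceeds .05.

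**Step 4. Logistic HIV-testing model.** Adjustment here changes the quantity estimated. With assumed testing of 30% in TAU, a conditional odds ratio of 2.0, the same prevalences, and each stratum factor carrying an odds ratio of 1.5, 2 or 3, the unadjusted odds ratio is 1.96, 1.90 or 1.80. The test of no effect stays valid either way, but the two odds ratios are not interchangeable.

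**The case against.** The strongest defence is that the SAP already covers this. It allows any necessary covariates and says it will consider them for precision, which is exactly the cost at issue. The power calculation never relied on the strata. Baseline use is already in the primary model, and .7 is the only correlation the documents give between repeated measures; if it applies to baseline as well, the loss is negligible. The documents also give no reason to expect CHF status or past admissions to predict days of use beyond baseline use. All of this stands as to size. What remains is that considering a covariate is not committing to it.

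Four stronger readings are tempting and are not supported:
- **That the trial is biased or underpowered.** Steps 1 to 3 show neither for the linear models.
- **That the SAP argues against covariates.** The sentence on randomization concerns covariates for reducing bias only, and the next sentence turns to precision in their favour.
- **That the open choice inflates the false-positive rate.** That would require choosing strata after seeing results, which neither document says will be done. The open covariate list is also wider than the strata.
- **That the loss is large for hospital days, because prior utilization is itself a stratum.** A model similar to the primary one would already carry baseline utilization, which the NSMOS collects at month 0. The further gain cannot be sized from the documents.

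The unstated Low/High cut and the CHF-specific utilization rule concern the allocation specification. For the analysis, using the values recorded at randomization settles both.

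**Conclusion.** The point holds as a modest matter of precision and prespecification. No SAP model names the stratification factors; they are allowed but not required. Omitting them from the linear models gives a valid, slightly conservative test, and planned power is met to within rounding. At an assumed R² of 5% to 20%, the standard error is about 2% to 11% larger than needed. The power forgone ranges from 0.2 points or less (r = .7) to about 1 to 6 points (V = .85).

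These sizes rest on assumed values for R², the baseline correlation, the urn rules and the stratum prevalences, and on an effect averaged over the two follow-ups. The absence of bias also assumes that dropout does not depend on the strata differently by arm. The change is worth making because it costs almost nothing and serves the SAP's own stated reason for using covariates.

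**What to change.** - **Each linear mixed model:** prespecify SUD severity, index condition and prior utilization as main-effect fixed effects, coded with the values recorded at randomization, plus the baseline value of that outcome. State the Low/High severity cut that allocation used.
- **Further covariates:** limit them to a list of pre-randomization variables fixed in advance.
- **HIV-testing logistic model:** decide in advance either to include the three main effects and report the odds ratio as conditional on them, or to report a standardized risk difference. Do not let the choice depend on how sparse the observed cells turn out to be.

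The cost is SAP wording and three degrees of freedom per linear model. The strata were needed for allocation, so no new data are required.

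### If urine and self-report disagree too often, the SAP moves the primary outcome to a urine result that has no alcohol test, and it does not define the rate that decides this

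*SAP*

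**What the plan says.** The SAP's primary hypothesis section builds the outcome from TLFB data: "we will create a variable for days of any substance use by combining all drug types and alcohol". Urine has a narrower role: "Urine samples collected at months 3 and 6 will be used to confirm reports of drug use". The two are linked by a condition: "Provided that the rate of disagreement between urine results and self-report is acceptable (below 15%), we will analyze days of substance use" as one variable. If the condition fails, the instruction is: "Should the rate of disagreement between urine and self-report exceed acceptable standards; we will analyze the urine results as the primary outcome". The only primary model named is a linear mixed model for days of use, with "any necessary covariates including the number of days of use reported at the baseline".

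Protocol item 7 describes the follow-up test: "Urine drug testing will be done using kits that test for cocaine, opiates, amphetamines, methamphetamines, benzodiazepines, cannabis, barbiturates, and PCP". The same item lists blood alcohol content, but only from hospital charts and only at baseline. Protocol item 9 admits a patient with an AUDIT score of at least 8 or a DAST score of at least 3, provided the MINI confirms a substance use disorder and the patient reports alcohol or drug use in the 60 days before admission. Alcohol alone can meet all three. The primary hypothesis in protocol item 2 is framed as self-reported days confirmed by urine.

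**The concern.** The fallback changes what the trial measures. The default outcome counts drinking days and drug days together, whereas the replacement sees drugs only. A trial that enrols people for drinking, and whose intervention encourages them to quit or cut down, could end with a primary outcome blind to drinking. It would also have left the protocol's own outcome, because urine alone is not urine-confirmed self-report.

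The decision rule adds to this. The SAP does not say whether disagreement is counted per patient, per sample or per drug. It does not say whether reported use with a negative sample counts, whether the drug must match, or which self-report days are compared with a sample. The SAP's model uses the past 30 days, the TLFB covers 90, and each visit has one urine sample. A truthful report of earlier use, or a prescribed drug, could therefore count as disagreement. Two analysts could choose different primary outcomes from the same data. The replacement itself has no coding, model or rule for missing samples.

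**Working it through.** **1. The plan's own power figure.** Inputs from protocol item 5 and the SAP: two-sided alpha .05, intraclass correlation .7, d = .4, 111 per arm, and "a 15% attrition rate by month 6, we will have 85% power to detect a moderate effect of the intervention".
- Effective n per arm = 111 × .85 = 94.35.
- Variance factor for the mean of two follow-ups = (1 + .7)/2 = .85.
- SE = √(2 × .85/94.35) = .1342.
- Power = Φ(.4/.1342 − 1.96) = Φ(1.02) = 84.6%.

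This reproduces the stated 85%. It applies to a continuous outcome (days of use) and says nothing about urine.

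**2. The two outcomes side by side.**

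| | Default | After the switch |
|---|---|---|
| Substances | all drugs and alcohol | eight drug classes, no alcohol |
| Source | TLFB | urine kit, months 3 and 6 |
| Model | linear mixed model | not stated |
| Power | 85% for d = .4 | not stated |

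**3. A drinking-only effect.** If the intervention reduces drinking and leaves drug use unchanged, the expected difference between arms in urine results is 0. The test then rejects with probability alpha, 5%, whatever the sample size. This follows from the content of the kit and needs no assumed rate.

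**4. The unit of the rate.** 222 × .85 = 188.7, about 189 patients. Two samples each give 378 samples, and eight drugs per sample give 3,024 results. The cut-off by patient is .15 × 189 = 28.35, so 29 patients reach it. Suppose 29 patients each have one discordant drug at one visit (an illustration, chosen to sit at the cut-off):
- by patient: 29/189 = 15.3%, switch;
- by sample: 29/378 = 7.7%, no switch;
- by drug result: 29/3,024 = 1.0%, no switch.

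**5. The direction of the rate.** Take an assumed table of 188 samples: 80 positive on both, 20 self-report only, 12 urine only, 76 negative on both.
- Both directions: 32/188 = 17.0%, switch.
- Unreported positives only: 12/188 = 6.4% of all samples, 12/88 = 13.6% of self-reported negatives, or 12/92 = 13.0% of urine positives. None of these switches.

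**6. Whether urine would be underpowered.** This needs figures that the documents do not give. Assume yes/no coding, 50% of TAU patients positive, correlation .7 between visits, and the same .4 SD shift on an underlying scale. The SCDM rate is then Φ(0 − .4) = .345.
- No covariate: SE = √([.25 + .226] × .85/94.35) = .0655; power = Φ(.155/.0655 − 1.96) = 66%.
- With a baseline covariate, the variance factor is .85 − .7² = .36; SE = .0426; power = 95%.
- If 25% of patients use alcohol only and are coded negative, both positive rates are multiplied by .75. The two powers become 47% and 82%.

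The answer falls on either side of 85% depending on the assumptions.

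**The case against.** The strongest defence is that the switch guards against inaccurate self-report. The SAP cites literature that self-report is generally accurate, so the trigger may never be met. If it is met, self-report has failed its check and an objective measure has a real rationale. For illustration, if SCDM patients under-reported by .2 SD with no true effect, the days test would reject about 32% of the time unadjusted (Φ(.2/.1342 − 1.96)) and 63% with a baseline covariate. That stands: keeping uncorrected self-report as primary at any level of disagreement would not be a good repair.

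A narrower reading is also possible, in which urine replaces only the drug component of the outcome. The SAP's words do not say this, but nothing else in the SAP excludes it.

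A reader might infer that the switch would leave the trial underpowered. The documents do not support that. The positive rates, coding and alcohol-only share are all assumed. Comparing urine with 84.6% for days also supposes that self-report keeps its full effect of .4 in exactly the case where it has failed its check. At d = .32, days power by the same formula is Φ(.32/.1342 − 1.96) = 66%, and the gap to the unadjusted urine figure disappears.

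A reader might also infer that alcohol-only patients would be scored as non-users. That is one coding. Because the urine outcome is undefined, leaving them out or analysing drug by drug is equally open. None of these codings measures drinking.

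**Conclusion.** The point holds and should be fixed. As literally written, the fallback produces a primary outcome that cannot show a change in drinking and departs from the protocol's urine-confirmed days of use. This rests on the text alone: the definition of the outcome, the kit's contents and the entry criteria.

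The 15% cut-off is stated, but how the rate is calculated is not, and that choice alone can decide the primary outcome (15.3%, 7.7% or 1.0% from one set of data). Those counts are illustrative; they show that the rule is not reproducible and do not predict that it will be triggered.

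The harm is conditional. A reader might infer that the primary analysis as a whole is unsound, but below 15% the SAP gives a clear rule (self-reported days, uncorrected) and the stated power reproduces. No power shortfall for the urine outcome is established.

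**What to change.** 1. Define disagreement as a urine-positive result for a non-prescribed panel drug with no TLFB use of that drug in a fixed window before the sample. State the window and the unit (for example, per sample), and report the rate by arm.
2. Below 15%, keep TLFB days as planned. At 15% or more, replace the switch to urine alone with one pre-specified primary outcome: urine-corrected days of any use. It keeps TLFB alcohol days, recodes unreported urine-positive records as use under one stated rule, and uses the same mixed model. An alternative recoding is a sensitivity analysis and should not be called a bound, because it cannot capture all unreported use.
3. Report urine positivity at months 3 and 6 with a logistic mixed model as a supportive outcome labelled drug use only. If baseline urine is a covariate, note that it mixes hospital toxicology with study kits (protocol items 6 and 7).

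The cost is SAP wording and analysis of data already planned: dated TLFB and urine (protocol item 7) and chart medications (item 13). Some limits remain. Unreported drinking, and drug use outside the urine detection window, stay unverified. The recoding window is a convention. Urine collection is unobserved (item 11), and hospital charts may miss outside prescriptions.

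The wording should be settled before the disagreement rate is calculated. The SAP is dated June 2017, after the funding period in the protocol ended, and the documents do not show whether the rate was already known. If it was, say so and report both the days and the urine results.
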